7.6.1.5 Assessment of Outcome

The outcome of an AE or SAE will be classified using the following outcome ratings:

0=Unknown

1=Recovered/resolved

2=Recovering/resolving

3=Not recovered/not resolved/ongoing

4=Recovered/resolved with sequelae

5=Fatal

7.6.1.6 Assessment of Causality

The Investigator will assess the relationship to IMP for all AEs and SAEs. The relationship will be characterized using the following causality ratings:

- **Probably related:** An AE with a reasonable time sequence to the administration of the IMP, unlikely to be attributed to concurrent disease or other drugs or chemicals, and that follows a clinically reasonable response on IMP discontinuation (de-challenge). Re-challenge information is not required to fulfill this definition.
- **Possibly related:** An AE with a reasonable time sequence to the administration of the IMP, but that could also be explained by concurrent disease or other drugs or chemicals. Information on drug IMP discontinuation may be lacking or unclear.
- **Not related:** An AE with a temporal relationship to drug administration that makes a causal relationship improbable, or in which other drugs, chemicals or underlying disease provide plausible explanations. There is no reasonable possibility that the event was caused by the trial treatment.
- **Not applicable:** This assessment can be used, for example, in cases where the patient did not receive any treatment with IMP.

7.6.1.7 Follow-Up of Adverse Events

All AEs should be followed until they have reached a final outcome (see [Section 7.6.1.5](#)) or the patient's participation in the trial ends, whichever comes first.

SAEs and Grade 3 (or severe), non-serious AEs that are assessed as "possibly related" or "probably related" to the IMP and that are still ongoing after ended trial participation, should be followed on a regular basis according to the Investigator's clinical judgment until a final outcome has been established.

The outcome "recovering" can be used as the final outcome for events that are stabilized (i.e., no further worsening is expected) and expected by the Investigator to resolve over time.

The outcome "not recovered" can be used as the final outcome for events that are not expected to resolve over time (e.g., cancer).

SAEs that are spontaneously reported by a patient to the Investigator after the patient has completed the clinical trial and for which a reasonable possibility of a causal relationship to the

IMP is assessed by the Investigator (“possibly” or “probably” related), should be reported to the Sponsor by the Investigator, regardless of the time that has elapsed (post-trial events).

7.6.2 Anticipated Risks and Safety Concerns of the Trial Drug

The most frequent ADRs reported during octreotide therapy include GI disorders, nervous system disorders, hepatobiliary disorders, and metabolism and nutritional disorders.

The most commonly reported ADRs in clinical trials with octreotide administration were diarrhea, abdominal pain, constipation, nausea, flatulence, headache, cholelithiasis, hyperglycemia and injection-site reactions. Other commonly reported ADRs were dizziness, biliary sludge, thyroid dysfunction (e.g., decreased thyroid stimulating hormone), loose stools, impaired glucose tolerance, vomiting, asthenia, and hypoglycemia (35).

7.6.2.1 Cardiovascular System

Bradycardia has been reported in patients treated with octreotide with a frequency ranging between 1% and 10% (35). Therefore, dose adjustment of medicinal products such as beta blockers, calcium channel blockers, or agents to control fluid and electrolyte balance may be necessary during octreotide administration.

7.6.2.2 Gallbladder and Related Disorders

Octreotide inhibits secretion of cholecystokinin, resulting in reduced contractility of the gallbladder and an increased risk of sludge and stone formation. Development of gallstones has been reported in 15 to 30% of long-term recipients of Sandostatin® IR. The prevalence of gallstones in the general population (aged 40 to 60 years) is about 5 to 20% (35). If gallstones do occur, management should be provided according to clinical guidelines.

7.6.2.3 Glucose Metabolism

Because of its inhibitory action on growth hormone, glucagon, and insulin release, octreotide may affect glucose regulation. Post-prandial glucose tolerance may be impaired. In some instances, persistent hyperglycemia may be induced as a result of chronic administration. Hypoglycemia has also been reported (35).

In patients with concomitant type 1 diabetes mellitus, octreotide can affect glucose regulation, and insulin requirements may be reduced. In non-diabetics and type 2 diabetics with partially intact insulin reserves, Sandostatin IR administration resulted in increases in post-prandial glycemia in some subjects.

7.6.3 Clinical Safety Laboratory Assessments

Clinical safety laboratory assessments will be performed at screening and during the trial at the time points outlined in Table 3.

A central laboratory will be used to analyze all laboratory evaluations. Details on the collections, shipment of samples, and reporting of results by the central laboratory will be provided separately. The results of the clinical safety laboratory assessments at screening must be reviewed before enrollment to assess the patient’s eligibility for the trial.

Laboratory values that are out of normal range must be evaluated for clinical significance. Clinically significant abnormalities known at time of signing the ICF should be reported on the Medical History eCRF page. Clinically significant findings must be discussed with the Medical Monitor before enrolling the patient in the trial.

New or worsened clinically significant findings occurring after signing of the ICF must be recorded on the AE eCRF page.

Blood samples for laboratory assessments will be taken after the assessment of vital signs and ECG (as described below).

Locally required tests, e.g., for SARS-CoV-2, may be performed and analyzed at local laboratories. Such tests will not be part of clinical trial assessments.

The assessments in [Table 4](#) will be performed:

Table 4: Clinical laboratory tests

Test category	Test name
Hematology	Hematocrit, hemoglobin, mean corpuscular hemoglobin, mean corpuscular hemoglobin concentration, mean corpuscular volume, red blood cell morphology, platelets, red blood cells, WBC, WBC with differential (basophils, eosinophils, lymphocytes, monocytes, neutrophils)
Biochemistry	Albumin, ALP, ALT, AST, amylase, bicarbonate, calcium, chloride, creatinine, cystatin C ^a , creatine kinase, GGT, lipase, plasma glucose, inorganic phosphorus, magnesium, potassium, sodium, total bilirubin (direct bilirubin and indirect bilirubin only in patients with total bilirubin >2×ULN), total cholesterol, low-density lipoprotein, high-density lipoprotein, total protein, triglycerides, blood urea nitrogen or urea, uric acid
Urinalysis	Urine dip-stick analyses at site (bilirubin, blood, glucose, ketones, WBC, pH, protein, specific gravity); further urinalysis (e.g., urine culture) by central laboratory, if indicated
Coagulation	Prothrombin time or INR, activated partial thromboplastin time
Thyroid	T3 (free), T4 (free), TSH
Additional tests	HbA1c

ALP: alkaline phosphatase; ALT: alanine aminotransferase; AST: aspartate aminotransferase; GGT: gamma glutamyl transferase; HbA1c: hemoglobin A1c; INR: international normalized ratio; TSH: thyroid stimulating hormone; ULN: upper limit of normal; WBC: white blood cells

a Only collected at specific visits as specified in [Table 3](#)

Pregnancy Tests

Women of childbearing potential will have a serum beta-human chorionic gonadotropin pregnancy test at screening. This will be performed by a central laboratory. The results of the pregnancy test at screening must be reviewed and confirmed to be negative before enrollment to assess the patient's eligibility for the trial. Moreover, urine pregnancy test will be performed at the other visits, as indicated in [Table 3](#). Urine pregnancy tests will be performed by dipstick locally. A positive pregnancy test requires immediate interruption of IMP treatment until the pregnancy is confirmed via a serum pregnancy test performed by a central laboratory. If confirmed positive, the patient must be withdrawn from the trial.

7.6.4 Immunogenicity Assessments

Blood samples for immunogenicity assessment of anti-drug antibodies will be taken according to [Table 3](#). Detailed method descriptions of the immunogenicity assays will be provided separately.

7.6.5 Vital Signs

Vital signs consist of body temperature, blood pressure (systolic and diastolic, mmHg), pulse rate (beats per minute), and respiratory rate (breaths/min) and will be collected at the time points outlined in [Table 3](#), following a resting period of at least 3 minutes. More frequent examinations

may be performed at the Investigator's discretion, if medically indicated. Vital signs will be measured before performing ECG and collecting blood samples.

Clinically significant findings that are known at the time of signing the ICF must be included on the Medical History eCRF page. Significant findings that begin or worsen after signing of the ICF must be recorded on the AE page of the eCRF.

7.6.6 Electrocardiogram

ECGs will be recorded and readings will be transmitted to a selected ECG central laboratory for analysis. Triplicate 12-lead ECG (3 ECG recordings at approximately 2-minute intervals) will be performed at each scheduled time point. The combined QTcF values from triplicate ECGs will be averaged to provide a single value for each patient. ECGs will be recorded at screening and at the time points outlined in [Table 3](#).

ECGs will be recorded after the patient has been resting in a supine position for at least 10 minutes. All ECGs should be recorded with the patient in the same physical position. ECGs will be recorded after vital signs and before blood samples for PK and clinical safety laboratory assessments.

The ECG assessments pre-dose and at the 24-hour time point have been selected to coincide with trough concentrations and near C_{max} of octreotide for CAM2029, based on PK results from trial HS-11-411. If at any visit QTcF ≥ 481 msec is observed, the procedures for QT-prolongation management described in [Section 17.1.2](#), Appendix 1 must be considered.

All ECG assessments will initially be assessed by the Investigator/qualified physician for any findings that require immediate medical attention. All ECGs will also be read by an ECG central reader. The clinical significance of any ECG findings will be determined by the Investigator, including after the central reading result is available. However, only ECG results provided by the central reader will be recorded in the clinical database.

Clinically significant abnormalities that are known at the time of signing the ICF should be reported on the Medical History eCRF page. Clinically significant findings must be discussed with the Sponsor before enrolling the patient in the trial. New or worsened clinically significant findings occurring after signing of the ICF must be recorded on the AE page of the eCRF.

7.6.7 Gallbladder Examination

Patients with symptomatic cholelithiasis at screening will be excluded from participating in the trial (see [Section 5.3](#)).

The gallbladder examination will be performed at screening, Week 77, Week 125 and at End-of-Treatment (Week 173) for all patients. These examinations can be performed at the trial site or at a local hospital. Information on the presence and location of gallstones, gallbladder sludge or other findings will be recorded on the appropriate eCRF page.

Scheduled MRI examinations of the liver and kidneys may be used for the safety assessments of the gallbladder at screening, Week 77, Week 125 and at End-of-Treatment (Week 173). If these MRI scans do not include satisfactory images, ultrasound of the gallbladder will be used.

Historical gallbladder imaging assessments performed within 4 months before Day 1, may be used as baseline measurement. If such a gallbladder ultrasound or MRI is available and includes satisfactory information on present gallstones, gallbladder sludge or other findings, the scheduled screening examination does not need to be performed.

Gallbladder examinations may also be performed at other time points during the trial if it is clinically indicated in patients showing symptoms of cholelithiasis. In those cases, ultrasound is the imaging technique of first choice.

Patients who have had a complete gallbladder removal do not need to undergo gallbladder examinations.

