4.2.1 Overall Trial Design

This is a Phase 2/3, randomized, placebo-controlled, double-blind, multi-center trial designed to evaluate the efficacy and safety of 2 treatment regimens of CAM2029 in patients ≥ 18 years old

with a diagnosis of symptomatic PLD, either in isolation as in ADPLD or in association with ADPKD.

The trial starts with a 52-week (12-month) placebo-controlled, Double-Blind Treatment Period with 2-dosing regimens of CAM2029. Results from trials with SRLs in patients with PLD have shown statistically significant effects on TLV and quality of life after 6 to 12 months of treatment (23, 24, 26, 27). Considering the high bioavailability of CAM2029, together with the inclusion of symptomatic patients with a minimum htTLV of 1800 mL/m (see Section 4.2.3), the probability of reaching significant treatment effects compared to placebo after the 52-week Double-Blind Treatment Period in this trial is considered high (see Section 8.2).

After the 52-week Double-Blind Treatment Period, all patients will be transferred to a 120-week, single-arm, Open-Label Extension Period, in which they will be treated with 10 mg CAM2029 every 2 weeks. Thereby, all patients will receive the active compound and have the opportunity to benefit from the treatment. The Extension Period will also allow monitoring of treatment efficacy and safety over a longer period and for a larger number of patients.

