- e Historical kidney volume will be collected, if available in medical records, in patients with confirmed ADPKD.
- f Serum pregnancy test at screening; urine pregnancy test at other visits.
- g Pre-dose.
- h Performed within 4 weeks prior to the Day 1 Visit.
- i Pre-dose and 24 ± 4 hours after dose.
- j Pre-dose and 24 ± 14 hours after dose.
- k Triplicate 12-lead ECG will be performed.

	Screening	Double-Blind Treatment Period ^a							
		D1	D8	D29	D85	D141	D169	D267	D365
Procedure/Assessment	W-12 to -1	W1	W2 ^b	W5	W13	W21	W25	W39	W53 ^c
Gallbladder examination ^l	X ^{m,n}								
MRI of liver and kidney volume and total liver cyst volume	X ^{h,o}				X ^p		X ^p		X ^p
Administration of IMP ^q		X	X	X	X	X	X	X	X
eGFR sampling (creatinine, cystatin C)	X	X ^g			X ^g		X ^g		X ^g
Plasma samples for octreotide measurement		X ^g			X ^r		X ^j	X ^g	X ^g
Immunogenicity		X ^g			X ^g		X ^g		X ^g
PLD-S	X	X ^g			X ^g	X ^g	X ^g	X ^g	X ^g
PLD-I	X	X ^g			X ^g	X ^g	X ^g	X ^g	X ^g
PGI-S	X	X ^g			X ^g	X ^g	X ^g	X ^g	X ^g
PGI-C					X ^g	X ^g	X ^g	X ^g	X ^g
SF-36		X ^g					X ^g		X ^g
PLD-Q		X ^g					X ^g		X ^g

- ^l Gallbladder imaging may be repeated during the trial if symptoms of cholelithiasis appear (ultrasound is first choice).
- ^m Historical gallbladder imaging assessments performed within 4 months before Day 1 Visit, may be used as baseline measurement. If such a gallbladder ultrasound or MRI is available and includes satisfactory information on presence of gallstones, gallbladder sludge or other findings, the screening gallbladder ultrasound does not need to be performed.
- ⁿ If the MRI of the liver and kidneys performed at screening, Week 77, Week 125 and Week 173/End-of-Treatment include satisfactory images of the gallbladder, these scans may also be used for the safety assessment by the Investigator.
- ^o The eligibility htTLV value will be calculated according to local clinical practice either using the MRI at screening or based on available historical imaging, as long as that the latter fulfils the imaging and schedule requirements of the trial (see footnote ^h and Section 7.3.1).
- ^p Visit window ± 3 days.

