7.5 Pharmacodynamic Assessment

7.5.1 Blood Collection and Handling

7.5.2 Analytical Method

7.6 Safety Assessments

7.6.1 Adverse Events and Serious Adverse Events

7.6.1.1 Adverse Event Definitions

An **AE** (synonym: adverse experience) is defined as any untoward medical occurrence associated with the use of a drug in humans, in a patient or clinical trial subject administered a trial treatment and which does not necessarily have a causal relationship with this treatment (i.e., whether or not considered drug-related). An AE can, therefore, be any unfavorable and unintended sign (e.g., an abnormal laboratory finding), symptom, or disease temporally associated with the use of a trial treatment, whether or not considered related to the trial treatment. Patients will be instructed to contact the Investigator at any time after enrollment if any symptoms develop.

Adverse drug reaction: All untoward and unintended responses to a trial treatment assessed as related to any dose administered.

AEs or SAEs assigned a causality assessment by the Investigator of “probably related” or “possibly related” will be considered by the Sponsor to be related for the purpose of defining adverse drug reactions and thereby also expedited reporting.

An AE is considered “unexpected” if the nature, severity, or outcome is not consistent with the reference safety information section in the current edition of the IB (33).

An **AESI** is defined as an AE that, regardless of severity of causal relationship, is specifically of scientific and/or medical concern to the Sponsor’s product or program, and for which ongoing monitoring and rapid communication by the Investigator to the Sponsor may be appropriate. Such AEs may require further investigation in order to understand and characterize them.

AESIs are predicted by the underlying PLD disease, the mechanism of action of CAM2029, or observation with other substances in the same class as octreotide. Many but not all selected events have been observed in non-clinical studies and/or clinical trials with CAM2029 and are defined based on the continuously ongoing review of the safety data.

The selected AESIs are listed under the following mechanistic groups:

- Arrhythmogenic potential and QT prolongation AEs
- Gallbladder related AEs
- Gastrointestinal related AEs
- Injection site reactions
- Hyperglycaemia related AEs
- Liver and renal cyst infection
- Pyelonephritis

AESIs will be collected through routine AE collection.

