8.9.2 Primary Efficacy Endpoint

The primary efficacy endpoint is change from baseline to Week 53 in htTLV as determined by MRI volumetry. In the analysis of the primary efficacy endpoint, the primary comparison will be between the average effect of the 2 CAM2029 doses compared to placebo. In addition, the 2 doses of CAM2029 will be compared with placebo separately, see [Section 8.10](#).

The primary efficacy endpoint will be analyzed using an ANCOVA model with fixed factor for treatment and baseline htTLV as covariate, within the framework of a multiple imputation method. Point estimates and the associated two-sided CI with 95% confidence level will be calculated for the difference in change. The absolute change analysis will be the primary analysis. In this ANCOVA model the average of the treatment effect of the 2 doses of CAM2029 (10 mg once weekly and 10 mg every 2 weeks) will be compared to placebo, i.e., the contrast for the treatment difference is $(0.5 \ 0.5 \ 0) - (0 \ 0 \ 1)$ where the 2 CAM2029 doses are given by the 2 first terms and placebo by the last. Additionally, each of the doses of CAM2029 will be compared with placebo separately, as described in the SAP.

The primary endpoint analysis will be performed when the last patient has completed the Double-Blind Treatment Period (Week 53).

The items that define the primary estimand are the following:

1. Treatment condition: The primary treatment condition of interest is the average effect of the CAM2029 treatment (10 mg once weekly and 10 mg every 2 weeks) vs placebo treatment. Thereafter, the treatment conditions of interest are the effects of:
 - CAM2029 10 mg once weekly vs placebo
 - CAM2029 10 mg every 2 weeks vs placebo
2. Target population: Patients in the ITT analysis set as defined by the inclusion/exclusion criteria in the trial.
3. Variable (endpoint): The variable addressing the primary clinical question is change from baseline in htTLV as assessed at Week 53.
4. Handling of intercurrent events: Intercurrent events will be handled through a combination of a treatment policy strategy and a hypothetical strategy depending on other treatment received and therapeutic interventions conducted while still in the trial:

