5.10.6 Additional Safety Assessments

5.10.6.1 Gallbladder Examination

Gallbladder imaging results details (location of gallstones, gallbladder sludge, or other findings) will be listed for each patient at each assessed visit.

[figure not shown]

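### No systematic gallbladder imaging read is planned under placebo control, although liver MRI is already scheduled at Weeks 13, 25 and 53

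*Protocol*

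**What the plan says.** Protocol 7.6.7 fixes the schedule: "The gallbladder examination will be performed at screening, Week 77, Week 125 and at End-of-Treatment (Week 173) for all patients". The gallbladder row of Table 3 agrees, as does Protocol 2.2.2. For reading the gallbladder from trial scans, 7.6.7 names the same visits, the final one included: "Scheduled MRI examinations of the liver and kidneys may be used for the safety assessments of the gallbladder at screening, Week 77, Week 125". Section 7.3.1 and Table 3 footnote n carry the same list.

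The Table 3 row "MRI of liver and kidney volume and total liver cyst volume" is marked at screening and at Weeks 13, 25 and 53 in the double-blind period. The Week 53 scan supplies the primary endpoint (Protocol 8.9.2): "The primary efficacy endpoint is change from baseline to Week 53 in htTLV as determined by MRI volumetry".

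Placebo control ends at Week 53. Protocol 4.2.1 says "all patients will be transferred to a 120-week, single-arm, Open-Label Extension Period". Section 4.1.3 narrows this to patients who did not stop IMP in the double-blind period and who can have injections at home.

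The protocol treats the gallbladder as a safety concern. Section 7.6.1.1 lists "Gallbladder related AEs" among the AESI groups. Writing about another octreotide product, Sandostatin IR, Section 7.6.2.2 says "Development of gallstones has been reported in 15 to 30% of long-term recipients". It gives 5 to 20% as the prevalence in the general population aged 40 to 60.

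For analysis, SAP 5.10.6.1 says that imaging details "will be listed for each patient at each assessed visit". Protocol 8.11.6 likewise plans only a listing.

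**The concern.** Stones and sludge can be silent, so counting them needs a planned look in every patient. The plan has such a look before treatment and then not until Week 77, when no untreated group remains. Three things are at stake.

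- **Attribution.** The protocol's two ranges, 15 to 30% and 5 to 20%, overlap between 15% and 20%. An uncontrolled frequency of, say, 18% would fit either, and a concurrent placebo group is what would separate them.
- **Regimen.** Protocol 4.2.4 includes the two-weekly arm to look for efficacy and safety differences between exposures. Week 53 is the last visit at which the arms are still on their randomized regimens.
- **Timing.** Under Protocol 2.2.2 and 11.3 the sponsor weighs benefit and risk for the extension on the 52-week data. Those data would contain no systematic gallbladder imaging after screening.

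**Working it through.** The plan gives no figure for this comparison, so there is none to reproduce. The first step sets the schedules side by side, and the second sizes what a Week 53 read could show.

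**Schedule.** Visits are from Table 3. Weeks since first CAM2029 dose are the visit week minus 1 for the active arms and minus 53 for former placebo patients in the extension.

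| Visit | Gallbladder examination | Liver MRI | Active arms: weeks since first CAM2029 | Placebo arm: weeks since first CAM2029 |
|---|---|---|---|---|
| Screening | yes | yes | 0 | 0 |
| Week 13 | no | yes | 12 | 0 |
| Week 25 | no | yes | 24 | 0 |
| Week 53 | no | yes | 52 | 0 |
| Week 77 | yes | yes | 76 | 24 |
| Week 125 | yes | yes | 124 | 72 |
| Week 173 | yes | yes | 172 | 120 |

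Under placebo control there are 3 scheduled post-baseline MRIs and 0 scheduled post-baseline gallbladder reads. At Week 77 the original arms differ only as 76 weeks against 24 weeks since first CAM2029, among patients who entered the extension.

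**Who is missed.** Patients who stop IMP are followed to Week 53 (Protocol 4.1.2 and 6.10.1) and cannot enter the extension (4.1.3). They therefore have no scheduled gallbladder examination after screening, although 7.6.7 speaks of all patients. A patient who withdraws consent may be asked to attend an End-of-Treatment visit (6.10.2), but that is not a systematic read.

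**Precision of a Week 53 read.** Protocol 8.2 gives 69 patients. With 1:1:1 allocation that is 69/3 = 23 per arm, so 46 active and 23 placebo. The 20 per arm used for power give 40 and 20. The documents give no 52-week incidence, so 25% on active and 10% on placebo are assumptions.

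SE = √[p₁(1 − p₁)/n₁ + p₀(1 − p₀)/n₀]

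- 46 v 23: √(0.1875/46 + 0.09/23) = √(0.00408 + 0.00391) = 0.089. The 95% CI is 15 ± 17.5 points, or −2.5 to +32.5.
- 40 v 20: √(0.1875/40 + 0.09/20) = √(0.00469 + 0.00450) = 0.096. The 95% CI is 15 ± 18.8 points, or −3.8 to +33.8.

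The table shows the range when other assumed frequencies are taken from within the 7.6.2.2 ranges, which are not 52-week incidences either.

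| Active v placebo | 46 v 23: CI half-width (points) | Fisher power | 40 v 20: CI half-width (points) | Fisher power |
|---|---|---|---|---|
| 15% v 5% | 13.6 | 15% | 14.6 | 10% |
| 22.5% v 12.5% | 18.1 | 13% | 19.4 | 11% |
| 30% v 20% | 21.0 | 10% | 22.6 | 9% |
| 30% v 10% | 18.0 | 42% | 19.4 | 37% |
| 30% v 5% | 16.0 | 72% | 17.1 | 64% |

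Only an extreme contrast would have a fair chance of reaching significance.

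**The case against.** A reader might infer that the randomized comparison is lost, or that gallbladder effects are never compared with placebo. The documents do not support either reading.

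- The Week 13, 25 and 53 scans are taken anyway and can be read later. The comparison is unplanned, not lost.
- Week 53 is not excluded. Protocol 2.2.2 has a general sentence, with no visit named, allowing the liver and kidney MRI to serve for gallbladder safety when image quality suffices.
- Some randomized data will exist. Gallbladder AESIs are collected in all arms and summarized under SAP 5.10.1. Section 7.6.7 allows imaging when symptoms appear. Section 7.3.1.1 requires incidental findings that may matter clinically to be recorded, as adverse events if after screening.

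What remains is narrower. The 2.2.2 sentence is permissive and attaches no record to Week 53. The other routes depend on symptoms or on a finding being thought important. None records that a gallbladder was seen and was clear, or could not be assessed, so there is no denominator.

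The objection on precision stands in full. The 46 and 23 are ceilings: withdrawals, removed gallbladders and unreadable scans reduce them, and patients with stones at baseline cannot contribute new ones. This limits the result to description but does not make a read of existing scans pointless.

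The objection on comparability also stands and shapes the fix. The baseline examination may be an ultrasound or historical imaging up to 4 months old (7.6.7). Central reading covers only liver, kidney and cyst volumes (7.3.1), and footnote n gives the gallbladder assessment to the Investigator.

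**Conclusion.** The point holds as a gap in a design choice. It is not an error or a contradiction in the documents. No systematic gallbladder imaging read is planned between Day 1 and Week 53. The first one afterwards comes when former placebo patients have had about 24 weeks of CAM2029, and it omits those who stopped IMP in the double-blind period. The partial data by arm do not systematically capture silent stones or sludge.

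The schedule finding rests on no assumption. The size of the benefit does: with at most 46 v 23 patients and assumed frequencies of 25% v 10%, the standard error is about 9 points, or nearly 10 with 40 v 20. Other assumed frequencies give 95% CI half-widths of about 14 to 23 points. The read would be a blinded, randomized but imprecise description of a named safety concern. The change is worth making because it costs little.

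**What to change.** 1. In Protocol 7.3.1, 7.6.7 and Table 3 footnote n, add Week 53 as a visit whose existing MRI, where taken, is read for gallstones or sludge and recorded as present, absent or not evaluable. Use the Investigator route that applies at the other visits, and add no ultrasound. Investigators stay blinded until the trial ends (6.5.2), so scans already acquired can still be read blind.
2. Read the screening MRI by the same rule, so that a new finding is defined on one modality. Exclude patients without a gallbladder.
3. In SAP 5.10.6.1, add a table of Week 53 findings and new findings by randomized arm, with the number evaluable and a 95% CI for the difference from placebo. Label it descriptive, in line with the general treatment of safety data in SAP 5.1.

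The cost is a few minutes of reading per patient, one eCRF item, one table and the document updates. There is no new scan, visit or staff. The downside is that some scans will not be evaluable and the intervals will be wide, which the table should show openly.
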